**STUDY SUMMARY:**

Investigational Agent(s) (Drugs or Devices)	N/A
IND / IDE / HDE #	N/A
Indicate Special Population(s)	 Children  Children who are wards of the state  Adults Unable to Consent  Cognitively Impaired Adults  Neonates of Uncertain Viability  Pregnant Women  Prisoners (or other detained/paroled individuals)  Students/Employees
Sample Size	Patients: N = up to 350 Providers: N = 20 Sexual and Gender Minority (SGM) supplemental study, Patients: N = approximately 100
Funding Source	National Institutes of Health
Indicate the type of consent to be obtained	 Written  E-consent via REDCap  Verbal/Waiver of Documentation of Informed Consent  Waiver of HIPAA Authorization  Waiver/Alteration of Consent Process
Site	 Lead Site (For A Multiple Site Research Study)  Data Coordinating Center (DCC)
Research Related Radiation Exposure	 Yes  No
DSMB / DMC / IDMC	 Yes  No

**OBJECTIVES**

STU00217126  
EH22-021

**Aim 1: Integrate routine clinical tests with PRO assessment to enhance screening, diagnosis, and management of patients with Benign Prostatic Hyperplasia (BPH).** PROs provide a cost-effective assessment strategy that can improve patient care by allowing for frequent surveillance and intervention. Men with BPH suffer from a variety of comorbid conditions (e.g., sleep disturbance, depression). We will use longitudinal modeling to identify risk factors and comorbidities that predict increased LUTS. Specifically, we will use PROs, developed by us in the LURN, to assess LUTS, including symptoms not captured by AUA-SI. We hypothesize that health variables from the PROMIS-29 Profile (e.g., sleep disturbance, depression, pain), when combined statistically with routine objective clinical variables (e.g., uroflowmetry, prostate size, intravesical prostatic protrusion) will provide unique predictive power for LUTS severity over time. Understanding these risk factors will facilitate preventative counseling and "just-in-time" interventions to improve in-clinic and telemedicine evaluations and treatment.

**Aim 2: To examine psychometric properties of the LURN SIs, including clinically meaningful differences in men with BPH receiving known effective treatment.** Longitudinal data will enable us to calculate effect sizes of the SI-10 and SI-29 from baseline to follow-up in the context of usual care, including guideline-driven treatment of BPH. LURN SIs will be anchored to patients' ratings of global change (PGI-I). A multiple-baseline design will allow estimation of test-retest reliability, while multiple longitudinal assessments provide quantitative estimates of minimally important differences (MIDs). We hypothesize that the SI-10 and SI-29 will have adequate test-retest reliability and precision to detect change across a range of severity in BPH in response to treatment.

**Aim 3: To create care-coordination recommendations to facilitate the matching of evidence-based treatments to patients with persistent symptoms using PROs.** PROs provide a patient-centered way to assess problems that may persist after treatment has been initiated. Many men discontinue medical treatment, and surgical treatments can lead to transient but distressing symptoms, including pain, urgency, and/or incontinence. These symptoms are not adequately captured by the AUA-SI. In addition, some patients may have persistent LUTS despite appropriate therapy that may be related to other health variables, as outlined in Aim 1.

We will use qualitative interviews with patients and providers to inform the creation of a care-coordination checklist that can be implemented in the medical record for patients with BPH. During the course of medical and/or surgical treatment for BPH, patients may have symptoms including pain, urgency, and/or incontinence. These symptoms are not adequately captured by the dominant questionnaire in the field – the American Urological Association Symptom Index (AUA-SI). In addition, some patients may have persistent LUTS despite appropriate therapy that may be related to other health variables. We plan to interview patients about their most important needs in between clinic visits to that we can develop better ways to follow these symptoms in between clinic visits using telehealth. We hypothesize that patient and stakeholder input will suggest care-coordination recommendations that will increase quality of care, in turn resulting in enhanced management (e.g., better recovery after surgery), improved quality of life, and decreased symptom bother for patients with BPH.

#### **Sexual and Gender Minority (SGM) Sub-Study**

**Aim 1: Determine psychometric properties of LURN SIs in SGM patients with BPH.** We hypothesize that the LURN SIs will demonstrate similarly large associations (Pearson  $r \geq 0.5$ ) with criterial measures, as well as sensitivity to known effective treatments (with-subject Cohen's  $d \geq 0.5$ ) in SGM patients with BPH.

#### **BACKGROUND:**

STU00217126  
EH22-021

LUTS attributable to BPH is one of the most common disease states, affecting approximately 30% of Medicare beneficiaries and costing over \$4 billion annually. In 2013, there were over 6.3 million office visits related to BPH for Medicare beneficiaries alone, and this number is expected to increase with the aging population. As the most common condition contributing to non-neurogenic LUTS in men, BPH is also the focus of frequently updated medical and surgical management guidelines that directly influence provider decision-making and patient care. Therefore, LUTS secondary to BPH represents an actionable, high-impact disease state and ideal target to build upon our work as part of LURN, wherein we created three novel questionnaires for use in patients with LUTS.

For decades, the AUA-SI questionnaire has been the PRO used in men with BPH, as recommended in the “Surgical Management” guidelines updated as recently as 2021. The AUA-SI, however, has several drawbacks that leave room for improvement. First, the AUA-SI omits UI and pain, which in the LURN cohort, was present in 51% and 17% of treatment-seeking men, respectively, despite exclusion of men with infection or urinary pain as a primary complaint. A significant proportion of men present with pain, and pain can be an important differential diagnostic marker (e.g., between BPH and chronic prostatitis). Second, it yields a single score for overall LUTS, which is laudable for simplicity, but may be insufficient when different symptoms are differentially impacted by treatment or have different relationships with biomarkers, diagnostic subgroups, etc. Third, the methodology used to develop the AUA-SI was specific to BPH, which is advantageous once the patient has been properly diagnosed, but patients presenting to the urology clinic may be suffering from other diagnoses, including kidney stones, infection, chronic prostatitis, pelvic floor dysfunction, stricture disease, and more. Thus, a questionnaire for the urology clinic should be general purpose and created with broad populations in mind.

With an awareness of the need to create an updated outcome tool in urology, our group – as part of the LURN – contributed to the creation of new questionnaires in urology, using state-of-the-art methods for the development of PROs. Our methodology included a comprehensive literature review, expert input from LURN investigators, and qualitative interviews with primary care doctors, urologists, urogynecologists, nurses (in primary care and specialty clinics), and a diverse sample of people with LUTS recruited from community and clinical settings. What is needed now is research connecting these new LURN questionnaires to actionable phenomena in the clinic. Toward this end, we will incorporate PROs into the routine care of patients with LUTS secondary to BPH. Reports provided to the physician will combine PROs with routine clinical tests (e.g., urinalysis, prostate size). Integrated PROs will allow for routine symptom surveillance without the need for the patient to return to the clinic, enhancing telehealth-based approaches.

### **STUDY ENDPOINTS:**

Aim 1: Longitudinal trajectories of LUTS in men treated for BPH. Serial symptom data will be collected over time using the LURN SI-29 (which includes the LURN SI-10 items) and the AUA-SI. Aim 1 will identify health variables from the PROMIS-29 Profile that predict trajectories of LUTS within the individual patient.

Aim 2: Test-retest reliability and minimally important differences in the LURN SI-29 subscales and the LURN SI-10. At the end of this study, we will have established the test-retest reliability of the LURN SI questionnaires and established minimally important differences in patients with BPH after known effective treatments.

Aim 3: A care-coordination checklist for monitoring of men treated for BPH. The goal of this project is to engage men with BPH and collect their open-ended input as to what symptoms, concerns, and challenges they face over the course of their treatment with BPH. In addition, 20 clinicians

STU00217126  
EH22-021

will also be interviewed. The end product will be transcripts from up to 40 men with BPH and 20 clinicians, and an accompanying code book.

**STUDY INTERVENTION(S) / INVESTIGATIONAL AGENT(S):**

Not applicable

**PROCEDURES INVOLVED:**

Patients will be recruited from urology clinics at Endeavor Health, in which both [name] and [name] are practicing physicians, and Northwestern Memorial HealthCare (NMHC) NM Gay and Bisexual Men's Urology Program Clinic. Recruited patients with BPH will undergo standard of care treatment as determined by their urologist. In this study, the maximum sample size will be 350. We aim to recruit a sample size of at least 300 analyzable participants, so we set the maximum sample size to 350 to account for participants who enroll but do not provide usable data (e.g., participants who complete only a baseline assessment and provide no other data). To obtain a sample that is roughly representative of BPH patients, as well as to generalize to patients receiving different kinds of treatment, the sample will be stratified by whether they are to receive medical/non-surgical management ( $n =$  up to 225) or procedural/surgical management ( $n =$  up to 125).

We created a battery of health measures to be specific to the management of BPH. The clinician will determine, on a case-by-case basis, the assessment schedule based on medical need, but sample schedules are presented in Tables 2.1 and 2.2 (medical management Table 2.1; surgical management Table 2.2). If a clinical follow-up visit is not required as part of standard of care as determined by the patient's personal physician (i.e., at Week 12 and Week 24 for medically managed patients), the follow-up visits can be completed remotely by phone, web, or app. Using PROs is already part of the management guidelines for BPH; the overarching hypothesis of this project is that a brief (i.e., clinically feasible) set of questions can aid in the management of BPH and can improve upon the existing method of the AUA-SI. We recognize that the proposed battery of measures is much longer than the one-page AUA-SI, but a longer battery of questionnaires is necessary for research purposes to clarify which measures would need to be dropped versus retained for use in the real-world clinic. In addition, scores from the one-page LURN SI-10 can be extracted from the longer 29-item questionnaire. Data analyses (see Section 1.4) will also include the LURN SI-10 score for maximum clinical relevance. Patients undergoing surgery will have more frequent queries in the immediate postoperative period (Table 2.2), as many men report bothersome symptoms of frequency, urgency, pain, and/or incontinence in this timeframe; thus, this period in particular is a target for better characterization and management of symptoms. We have had success with collecting data every 2 weeks as part of other research, supporting feasibility. Routinely collected objective clinical data, including urinalysis, prostate-specific antigen, uroflowmetry, post-void residual, prostate size, intravesical prostatic protrusion, and cystoscopic findings will also be collected and analyzed in combination with PROs.

For assessment of test-retest reliability, patients will receive the LURN SI-29 and AUA-SI questionnaires in two instances, 2 weeks apart. 60 patients will be needed for test-retest reliability; therefore, participants will be approached until 60 patients have completed 2 scorable questionnaires. Patients consented prior to their baseline clinic visit will complete the questionnaires 2 weeks (range 1-3 weeks) prior and then again at the visit, while patients who enroll at the baseline visit and have a scheduled diagnostic procedure at least 1 week but no longer than 3 weeks later (e.g., cystoscopy and/or prostate transrectal ultrasound), with no

STU00217126  
EH22-021

treatments or interventions planned in the interim, will complete questionnaires at the baseline clinic visit and again 2 weeks (range 1-3 weeks) later. In this latter group of patients, we expect the lowest variation in symptoms over time due to minimal change in circumstances. In order to effectively assess test-retest reliability, we will target 2 weeks between questionnaire administration but will allow a 1-3-week time interval between questionnaires. The questionnaires will be delivered in Epic MyChart but could also be completed on paper or over the telephone; research coordinators will contact participants to remind them of these questionnaires in order to minimize missing data. Mode of administration will be recorded.

Table 2.1 Study questionnaires, medical/non-surgical intervention (Schedule of assessments: baseline, inter-visit follow-up, and clinic assessments)									
	# Items	Week -2	Baseline (clinic)	Week 4	Week 8	Week 12 (clinic)	Week 16	Week 20	Week 24 (clinic)
LURN SI-29	28								
PROMIS-29 Profile	29								
AUA-SI	8								
Patient Global Impression of Improvement (PGI-I)	1								
National Cancer Institute Quick Food Scan	17								
3-Day Voiding Diary	9								
PROMIS-GI: Constipation	9								
PROMIS-GI: Diarrhea	6								
SHIM	5								
MSHQ-EjD	4								
STOP-BANG	8								
PRO Cognitive Function – Short Form 4a	4								
Patient Feedback Survey (optional)	6								
Note: Study time points (e.g., Week 4, Week 8) are approximate – Participants will be given a time window of $\pm$ 2 weeks. The minimum time between assessments will be approximately 4 weeks. Time windows may be adjusted based on COVID-19 protocols (e.g., if a clinic visit is converted to telehealth).									

STU00217126  
EH22-021**Table 2.2 Study questionnaires, surgical/procedural intervention  
(Schedule of assessments: baseline, inter-visit follow-up, and clinic assessments)**

	# Items	Baseline (clinic)	Preop **	Week 1	Week 2	Week 4 (clinic)	Week 6	Week 8	Week 12 (clinic)	Week 24 (clinic)
LURN SI-29	28									
PROMIS-29 Profile	29									
AUA-SI	8									
Patient Global Impression of Improvement (PGI-I)	1									
National Cancer Institute Quick Food Scan	17									
3-Day Voiding Diary	9									
PROMIS-GI: Constipation	9									
PROMIS-GI: Diarrhea	6									
SHIM	5									
MSHQ-EjD	4									
STOP-BANG	8									
PRO Cognitive Function – Short Form 4a	4									
Patient Feedback Survey (optional)	6									
Note: Study time points (e.g., Week 4, Week 8) are approximate – Participants will be given a time window of $\pm$ 2 weeks. The minimum time between assessments will be approximately 4 weeks. Time windows may be adjusted based on COVID-19 protocols (e.g., if a clinic visit is converted to telehealth). ** If surgery is not immediately scheduled, complete questionnaires every 4 weeks until surgery is scheduled.										

To assess MIDs, we will administer the PGI-I as a measure of global change at each post-baseline time point. The PGI-I is a single-item questionnaire that asks respondents to rate their condition compared with prior to treatment on a 7-point scale from very much worse (1) to very much better (7). LURN SI-29 and SI-10 scores at 12 weeks post-baseline will be used to assess changes in scores since baseline.

In addition, participants will be offered the opportunity to complete a patient-response burden questionnaire (patient feedback survey) at the end of their study participation. This will provide a better understanding of how the participants perceived the PROs.

STU00217126  
EH22-021

**Uroflowmetry.** Uroflowmetry is a test that measures the flow rate of urination while the patient is voiding. It also quantifies the voided volume. Uroflowmetry is usually captured during routine care with a urologist, but sometimes it is not deemed necessary or logistically challenging to obtain during routine clinical care (for example, the patient voids before being seen in clinic). In this study, if the patient does not receive a uroflowmetry test as part of routine care, we may include it as a research activity. In this case, the patient will receive instructions from the research coordinator on how to do the test. To ensure that the patient does not have an empty bladder for the test, the coordinator will ask the patient to drink some water from water bottles provided in the clinic space, while the study is being explained to them. If possible, the patient will be asked not to void until the uroflowmetry test. They will then do the test in a private restroom at the clinic. For uroflowmetry, the patient simply voids into a funnel which measures voided volume and urine flow rates. At the end of the test, a printed readout is produced, which will be stored in a locked filing cabinet. A bladder scan (handheld ultrasound) may then be performed to measure the post-void residual volume. The research coordinator will enter the necessary values from the printed report into REDCap. There are no risks associated with uroflowmetry, as it involves voiding of urine. The test takes less than 5 minutes to complete.

The data set from the LURN I study, funded by the NIDDK, will be used as a comparator dataset: it will be incorporated into the visualization graphs to offer a comparative baseline and will also be utilized to compare and contrast findings from our study data.

**Crossover between treatment management arms:** If a participant in the medical management arm decides to undergo surgery during their routine clinical care, they are allowed to switch to the surgical management arm. At that point, the participant's timeline is restarted based on the treatment type. Similarly, participants enrolled in the surgical management arm that do not complete surgery will be moved into the medical management arm if they are using medical treatment.

**Minimizing missing data: Alternate data collection strategies.** The primary mode of data collection will be patients completing surveys administered electronically via Epic MyChart. There may be some patients who are unable to complete their questionnaires electronically due to a low level of technological literacy or other information technology issues. In such cases, they will be offered the chance to complete the questionnaires via paper packets, which will be administered in the same order as the electronic questionnaires. We will use the 29-item version of the PROMIS Profile, version 2.1. If a patient in this study has difficulties with both electronic and paper questionnaires, a research coordinator will read the questionnaire to the participant, including response options, and record their responses for inclusion in the analyses.

**Interviews.** To maximize convenience for participants (patients and providers), interviews will be conducted via telephone or secure end-to-end encrypted virtual interview (e.g., Zoom) by a trained interviewer. Participants' email addresses and phone numbers will be shared with the interviewer. Providers will be recruited from across the United States through email invitations and consented verbally before the interview. These invitations will include detailed information about the study's purpose, procedures, and the voluntary nature of participation. A trained researcher will use a qualitative interview guide to ask questions regarding healthcare coordination gaps. Interviews will be audio-recorded and transcribed. Audio recordings of interviews will be transcribed using a HIPAA-compliant service, such as "TranscribeMe." These recordings will not contain any identifiable information, ensuring participant confidentiality. The recordings will be securely transferred to the transcription service through an encrypted platform.

STU00217126  
EH22-021

Once the transcriptions are completed and securely returned, the transcription service will delete the audio recordings from their system. Transcriptions will be stored on a secure system (Box.com) accessible only to the research team, and all files will be reviewed to confirm the absence of any identifying details.

Interviews will be transcribed and imported into qualitative analysis software. The team will review a sample of five transcripts to create an initial codebook to capture themes mentioned by participants. Trained research assistants will then independently code one transcript, and then meet again to refine the initial codebook. Each transcript will be coded carefully by two trained team members applying codes. This process will be iterated throughout the analysis timeline to process new information and themes as they arise. Themes, concerns, and symptoms from the qualitative interviews will be used to determine prevalent topics for inclusion in a care-coordination checklist.

Each interview is expected to be less than 60 minutes. Participants will be interviewed at three time points: baseline, post-treatment, and follow-up. If we continue to observe new themes upon examining the qualitative data for 20 participants' interviews, then we will add interviews, two at a time until saturation is reached. We plan to interview no more than 40 patients.

For providers, each interview is expected to be less than 20 minutes. Providers will be interviewed once throughout the study period. We plan to interview up to 20 providers. Provider interviews will include topics such as care coordination for men with BPH and data visualization for symptom questionnaires. During these interviews, different data visualization formats will be shared with providers to solicit their feedback on the clarity, usability, and overall preference for each format. The aim is to identify which visualization methods best support clinical decision-making and enhance the interpretation of patient-reported symptom data in routine practice.

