Shortly after the participant is consented into the study, they will receive PROs for the baseline or pre-baseline visit. PROs will be collected in accordance to the study schedule set forth for surgical or medical management, or the SGM substudy.

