## COMPENSATION FOR PARTICIPATION IN RESEARCH ACTIVITIES

### ***At Endeavor Health:***

Participants will receive a sum of \$60 in compensation for their time and effort by the completion of the study. They will be compensated after each completed study interaction as follows:

	Visit 1 (Baseline)	Visit 4 (12 Weeks Post-Treatment)	Visit 7 (24 Weeks Post-Treatment)	
Medical Management	\$20	\$20	\$20	
	Visit 1 (Baseline)	Visit 5 (4 Weeks Post-Procedure)	Visit 8 (12 Weeks Post-Procedure)	Visit 9 (24 Weeks Post-Procedure)
Surgical Management	\$15	\$15	\$15	\$15

Participants will receive their payments in the form of gift cards at the end of each completed clinical visit. Participants who complete audio-recorded interviews will receive an additional \$40 after each interview (at baseline, post-treatment, and follow-up) for a sum of \$120 for three interviews. Providers will receive a compensation of \$100.

STU00217126  
EH22-021

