**DATA MANAGEMENT AND CONFIDENTIALITY**

Data will be extracted from the EHR and de-identified. Study logistical data will be stored in REDCap, only accessible to authorized users. The PIs will train all staff on confidentiality and working with sensitive data.

STU00217126  
EH22-021

Patient-facing study-specific activities include collection of patient-reported outcomes (PROs) and measurement of height, weight, and neck and waist circumferences that follow the schedule of assessments. The patients will undergo standard of care treatment as determined by their urologist – medical management or surgical management. Data routinely collected during clinical practice and part of EMR will be collected for this study.

The Endeavor Health, University of Chicago, and Northwestern REDCap database will be set up for this study and will be used for data collection. Northwestern University and University of Chicago will have access to this database for data review and data analysis throughout the study.

Clinical data and patient-reported outcomes (PROs) will be extracted from Epic via chart review, the Enterprise Data Warehouse (EDW) and Clinical Data Interoperability Services (e.g., REDCap-Epic integration). Data will be extracted via Epic chart review and patient-reported outcomes at baseline as well as at follow-up visits. These data include: date of tests/exams, date of birth, sex, gender, sexual orientation, race, ethnicity, education, marital status, family history of BPH or PCa, sexual activity, employment status, health insurance, prior BPH surgeries, BPH treatment plan, type and date of BPH surgery (surgical management), chief complaint as identified by the treating urologist, relevant current medications (i.e., alpha blockers, 5-ARIs, PDE5is, anticholinergics, B3 agonists, antidepressants, anxiolytics), comorbidities (i.e., DMI or DMII, depression, anxiety, hypertension, obstructive sleep apnea), substance use (i.e., caffeine, alcohol, tobacco), height, weight, neck and waist circumferences, laboratory tests (i.e., urinalysis, PSA, PHI, A1c, total cholesterol, HDL, LDL), urodynamics (i.e., uroflowmetry, UroCuff, PVR), prostate size, and intravesical prostatic protrusion.

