## **ECONOMIC BURDEN TO PARTICIPANTS**

As this is an observational study, all clinical activities are part of usual care and no additional costs will be incurred by participants. PRO monitoring will occur remotely and will not incur travel costs. Because interviews can be completed by phone, there is no cost of travel, parking, etc. The main cost to participants is their time, for which they will be compensated.

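### The Table 2.2 note sets a 4-week minimum interval that its own columns cannot meet, and the protocol is unclear whether the clinician or the study sets the questionnaire schedule

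*Protocol*

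**What the plan says.** On who sets the schedule, Procedures Involved states: "The clinician will determine, on a case-by-case basis, the assessment schedule based on medical need, but sample schedules are presented" in Tables 2.1 (medical) and 2.2 (surgical). Both tables are headed as study questionnaires and as the schedule of assessments. The same section goes on to say that if no clinic visit is needed at Weeks 12 and 24 for medically managed patients, that follow-up can be done remotely. It adds that surgical patients will be queried more often soon after the operation, as in Table 2.2.

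Elsewhere the tables act as the study's own schedule:
- Below Table 2.2: "we will administer the PGI-I as a measure of global change at each post-baseline time point", and "LURN SI-29 and SI-10 scores at 12 weeks post-baseline will be used to assess changes in scores since baseline".
- Consent Process: "PROs will be collected in accordance to the study schedule set forth for surgical or medical management".
- Compensation: payments attach to numbered visits at stated weeks.
- Data Management and Confidentiality: lists PRO collection as a study-specific activity, together with "measurement of height, weight, and neck and waist circumferences that follow the schedule of assessments".

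On spacing, the notes under both tables carry the same rule: time points are approximate, the window is ±2 weeks, and "The minimum time between assessments will be approximately 4 weeks".

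**The concern.** The spacing note suits Table 2.1 but not Table 2.2, which has assessments one or two weeks apart after the procedure. A coordinator who applies the note would have to skip or move early postoperative assessments. That is the period the protocol singles out for better description of symptoms.

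The sentence on clinician discretion raises a different question. If medical need sets when research questionnaires are sent, observation times can depend on how the patient feels. The Aim 1 endpoint is the longitudinal course of LUTS, and trajectory estimates can be biased when timing depends on current or unrecorded symptoms. Site staff cannot tell from the text which rule governs, and could follow either one and claim compliance.

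**Working it through.** **Spacing in Table 2.2.** Inputs, all from the table and its note: post-procedure columns at Weeks 1, 2, 4, 6, 8, 12 and 24; minimum interval about 4 weeks; window ±2 weeks. The cells that assign instruments to columns are not readable in the text, so I take each column as an assessment. The PGI-I rule supports this.

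1. Gaps: 2−1 = 1, 4−2 = 2, 6−4 = 2, 8−6 = 2, 12−8 = 4, 24−12 = 12. Four of six are under 4 weeks.
2. Windows: Week 1 covers −1 to 3, Week 2 covers 0 to 4, Week 4 covers 2 to 6, Week 6 covers 4 to 8 and Week 8 covers 6 to 10. Each adjacent pair overlaps, and the Week 1 window starts before the procedure.
3. The number of assessments that fit in a span S with minimum interval m is at most 1 + floor(S/m). For the five columns in Weeks 1 to 8, S = 8−1 = 7 at nominal weeks. With full windows starting no earlier than the procedure, S = 10−0 = 10.

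| Minimum interval | Nominal weeks | Full windows |
|---|---|---|
| 4 weeks | 1 + floor(7/4) = 2 (e.g. Weeks 1 and 6) | 1 + floor(10/4) = 3 (e.g. times 0, 4, 8) |
| 3 weeks (loose reading) | 1 + floor(7/3) = 3 (Weeks 1, 4, 8) | 1 + floor(10/3) = 4 (times 0, 3, 6, 9) |

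The examples show that each bound is reached. All five fit at nominal weeks only if the minimum is 1 week or less. With full use of the windows they fit only if it is 10/4 = 2.5 weeks or less.

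4. Table 2.1 for comparison: follow-up columns 4, 8, 12, 16, 20 and 24, so every gap is 4 weeks and the note fits. Its Week −2 column is 2 weeks before Baseline, but the test-retest text gives that interval its own range of 1 to 3 weeks.

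**Who sets the schedule.** This is a comparison of text, with one count. Numbering the columns of Table 2.1 from Baseline (leaving out Week −2) makes Week 12 Visit 4 and Week 24 Visit 7. Numbering Table 2.2 from Baseline (counting Preop as Visit 2) makes Week 4 Visit 5, Week 12 Visit 8 and Week 24 Visit 9. With Baseline as Visit 1 in each arm, all seven visit numbers in the compensation tables match. The payment scheme therefore counts the table columns as actual visits.

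The most direct conflict is between Procedures Involved and Consent Process: one gives the schedule to the clinician and the other to the study. The PGI-I and 12-week rules also presuppose set time points. The compensation section supports this indirectly. Data Management is weaker support, because its phrase about following the schedule may attach only to the body measurements. No section says which statement governs.

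**The case against.** The strongest reply is that the protocol's intent is clear. The sentence on remote completion keeps Weeks 12 and 24 for medically managed patients whether or not a visit is needed, so what varies with medical need appears to be the clinic visit. MyChart is the primary mode of collection, with paper and coordinator-read alternatives, and Economic Burden states: "PRO monitoring will occur remotely and will not incur travel costs". On spacing, the note looks copied from Table 2.1, says only approximately, and sits beside text that plainly wants frequent postoperative queries and cites two-weekly collection as feasible.

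Much of this stands. The fixed reading is probably the intended one, and few coordinators would drop early assessments because of a general note. But the remote sentence names only the medical arm's Weeks 12 and 24, and nothing limits the clinician's discretion to visits. The spacing note is wrong as written for Table 2.2 even with approximately read as 3 weeks.

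A reader might infer that the study plans symptom-driven assessment and that Aim 1 is therefore biased. The documents do not support that. No section describes such timing, and the analysis model is in the SAP, which was not available. If timing depended only on recorded scores, a likelihood-based analysis would show little or no bias. A reader might also infer that the 12-week score for Aim 2 is at risk throughout. That goes too far: Week 12 is expressly kept for medically managed patients, and for surgical patients it is a table column and a paid visit.

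**Conclusion.** Both inconsistencies are real, and both are minor. The Table 2.2 note cannot be satisfied by that table: 4 of 6 post-procedure gaps break the stated minimum, and at most 2 of 5 early assessments fit at nominal weeks, or 3 with full windows. These counts assume that the note is applied literally and that each column is an assessment; they describe a drafting error, not expected data loss. The clinician-discretion sentence contradicts the sections that treat Tables 2.1 and 2.2 as the study schedule. The size of any bias cannot be derived from the protocol and none is claimed; the risk to the Aim 1 trajectories is conditional on that sentence being followed literally for research questionnaires. Neither point is a matter to leave to the SAP, since both are operational rules that the protocol itself states.

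**What to change.** 1. Replace the note under Table 2.2 with a minimum interval and windows of its own that are compatible with Weeks 1, 2, 4, 6 and 8 and do not overlap. Leave the Table 2.1 note for its follow-up columns. The pre-operative rule (every 4 weeks until surgery is scheduled) is unaffected.
2. Reconcile the discretion sentence in Procedures Involved with Consent Process and with the PGI-I and 12-week rules, by stating whether the clinician's discretion covers clinic visits only or the research questionnaires as well. If visits only, say that research PROs follow the study schedule, with remote completion when no visit takes place, and that any extra questionnaire is recorded as unscheduled. The wording should not detach questionnaires from visits altogether: several columns are marked as clinic time points, and one test-retest group completes its second questionnaire at the baseline visit.

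The cost is one or two sentences and one corrected note. MyChart, paper and telephone completion and coordinator reminders are already planned, so no new procedure is needed.
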